### 5.3 Prohibited Medications

- Investigational agents
- Cytotoxic chemotherapy
- Systemic immunosuppressive medications
- Systemic glucocorticoids (topical steroids are allowed; inhaled/nasal steroids are allowed only if the participant is not also receiving HIV protease inhibitors)
- Anabolic steroids (physiologic testosterone replacement therapy is not exclusionary)
- Hepatitis C medications

## 6.0 CLINICAL EVALUATIONS

### 6.1 Schedule of Events

Evaluation	Screening Visit	Entry/Randomization Visit (within 60 days of positive ISI screening)	Interventions: SHUTi vs. Sleep Education/Hygiene Active Control	Week 12 Visit (70-120 days after Entry Visit)	Week 24 Visit/Closeout (150-210 days after Entry Visit)
Verbal Informed Consent for Screening	X				
Written Informed Consent for Randomization		X			
Documentation of HIV Status	X				
Medical/Psychiatric History	X				
Medication/Supplement Use History	X				
Diagnoses	X				
Laboratory History [hepatitis C antibody status (positive, negative), hepatitis C RNA level (HCV viral load), hemoglobin, glucose, albumin, creatinine, and estimated GFR (per CKD-EPI equation)]		X			
Updated Psychiatric Treatment History		X		X	X
Updated Medications		X		X	X
Updated Diagnoses		X		X	X
Height (in cm)		X			
Weight (in kg)		X		X	X
Vital Signs (blood pressure, heart rate, temperature)		X		X	X
Screening laboratories (HIV-1 RNA) 	X	X			
HIV-1 RNA and CD4 cell count		X		X	X
Inflammation biomarkers (hsCRP, IL-6, sCD14, sCD163, CD14+CD16+ monocytes)		X		X	X
Urine pregnancy testing		X		X	X
Archived blood samples		X		X	X
Screening ISI 	X				
Questionnaires: ISI; PSQI; DBAS-16; PHQ-9; SCL-20; GAD-7; PROMIS® Fatigue Short Form; AUDIT; PEG-3; and SF-36		X		X	X
STOP-BANG Sleep Apnea Questionnaire		X			
Sleep History and Beliefs Survey (PRE-Treatment)		X			
Sleep History and Beliefs Survey (Post-Treatment)				X	X
Alcohol, tobacco, substance use; physical activity; medication adherence questionnaires		X		X	X
SCISD-R		X			
Sleep Diaries		X (14 days after)		X (14 days before)	X (14 days before)
Randomization		X			
SHUTi vs. Active Control Interventions			X		

The HIV-1 RNA screening laboratory can be abstracted from routine clinical care if performed within 42 days (before or after) the Screening ISI used for determining eligibility. If HIV-1 RNA is not available from routine clinical care within this window around the Screening ISI, then the participant must complete an in-person Screening Visit for blood HIV-1 RNA measurement.

The Screening ISI can be performed by phone to assess eligibility after verbal consent is provided. If the ISI score is <11, then the patient is not eligible for the study. If the ISI score is  $\geq 11$ , then the participant may be eligible.

## 6.2 Definitions for Schedule of Events – Special Instructions and Definitions of Evaluations

### 6.2.1 Documentation of HIV-1 Infection

HIV-1 infection documentation must be present in the source documentation at the Entry Visit. HIV-1 infection, documented by both: (1) any licensed rapid HIV test or HIV enzyme test kit at any time prior to study entry and (2) by at least one detectable HIV-1 antigen or at least one detectable plasma HIV-1 RNA viral load.

### 6.2.2 Medical/Psychiatric History

A medical/psychiatric history must be present in the source documents. Record the following on CRFs at the Screening Visit:

- Birthdate
- Sex at birth
- Patient's self-report of ethnicity (Hispanic vs. Non-Hispanic) and race (White, Black, Asian, Native American, Pacific Islander)
- Year of initial documentation of HIV positivity
- Route of HIV infection (heterosexual contact, same sex contact, injection drug use, blood transfusion)
- Diagnoses (all medical and psychiatric)

### 6.2.3 Medication/Supplement Use and Psychiatric Treatment History

A medication history must be present in source documents. The following information will be recorded on the CRFs at the Screening Visit:

- Start dates of current antiretroviral treatments
- Start dates of current insomnia and antidepressant treatments
- Any other prescription medications within 30 days of Entry Visit
- Any supplements (non-prescription) used within 30 days of Entry Visit
- Any behavioral treatments within one year of Entry Visit

### 6.2.4 Diagnoses/Updated Diagnoses

All confirmed and probable new diagnoses will be recorded on the CRFs, including current status at the time of the study visit.

### 6.2.5 Updated Medications

All new and/or discontinued prescription medications (including insomnia and antidepressant medications) taken since the Entry Visit will be recorded on CRFs with start and stop dates.

### 6.2.6 Clinical Assessments

#### 6.2.6.1 Height

Height in cm will be recorded on CRFs at the Entry Visit.

#### 6.2.6.2 Weight

Weight in kg will be recorded on CRFs at Entry, Week 12, and Week 24 study visits.

#### 6.2.6.3 Resting Blood Pressure

Blood pressure measurements (systolic and diastolic) will be recorded on the CRFs at Entry, Week 12, and Week 24 study visits. Blood pressure measurements should be performed on the same arm throughout the study. The participant will first sit quietly for five minutes. With the elbow and forearm resting comfortably on a flat table, the blood pressure should then be measured. After two minutes, repeat blood pressure measurement on the same arm. After another two minutes, repeat blood pressure measurements again. Therefore, three blood pressure measurements are to be documented in the CRFs.

#### 6.2.6.4 Resting Heart rate

Resting heart rate measurements will be recorded on the CRFs at Entry, Week 12, and Week 24 study visits. This may be done prior to the first blood pressure measurement. The participant will first sit quietly for five minutes prior to measurement of heart rate.

#### 6.2.6.5 Laboratories obtained through routine clinical care

Laboratories obtained through routine clinical care before the Entry/Randomization visit will be abstracted and recorded onto CRFs. These include most recent hepatitis C antibody status (positive, negative), hepatitis C RNA level (HCV viral load), hemoglobin, glucose, albumin, creatinine, and estimated GFR (per CKD-EPI equation). If available, the most recent HIV-1 RNA level obtained within 30 days of the positive ISI score meeting the insomnia inclusion criterion will also be recorded on CRFs.

#### 6.2.6.6 Laboratories

An HIV-1 RNA level will be obtained at an in-person Screening visit if none are available through routine clinical care within 30 days of the positive ISI score meeting the insomnia inclusion criterion. This will be performed at the IUH Pathology Laboratory.

HIV-1 RNA and CD4 cell counts will be measured at the Entry, Week 12, and Week 24 study visits. These will be performed at the IUH Pathology Laboratory.

Whole blood [THREE (3) 6.0-mL, purple-top EDTA tubes] will be drawn for the inflammatory biomarker measurements at Entry, Week 12, and Week 24. These tubes are to be filled completely. These whole blood samples are not to be spun after collection and are to be kept at room temperature and upright pending transfer to the Angio BioCore. These 3 tubes for the Angio BioCore will be labeled "WB ABC". These will be given to the Angio BioCore laboratory (under [name] supervision) for same day measurement of monocyte fractions using standard flow cytometry procedures. The residual sample will be processed for plasma aliquots and stored. These aliquots will later be used for batch testing of hsCRP, IL-6, sCD14, and sCD163 in the Analyte Core of the Diabetes Center (under [name] supervision) and for longer term archival for measurement of proteins and chemicals of future research interest.

Computer labels will be generated and affixed to the appropriate specimen containers and will include the specimen number, participant number, specimen date, specimen type, and aliquot number. Labels must be affixed prior to freezing the vials.

Urine pregnancy testing will be performed for women of reproductive potential at Entry, Week 12, and Week 24.

## 6.2.6.7 Questionnaires

At Entry, Week 12, and Week 24, participants will complete a questionnaire battery (see Appendix) containing the following: standard questions assessing demographics, medical/psychiatric history, sleep medication use, insomnia treatment satisfaction, and insomnia care received outside of the trial; ISI; PSQI; DBAS-16; PHQ-9; SCL-20; GAD-7; PROMIS® Fatigue Short Form; AUDIT; PEG-3; and SF-36. The questionnaire battery will also include validated scales assessing physical activity level, tobacco use, illicit drug use, medication adherence and the probability of sleep apnea (STOP-BANG Questionnaire; Entry only). The questionnaire battery will be administered on a computer in private with availability of the study team to assist only when asked by the participant.

## 7.0 ADVERSE EVENT MANAGEMENT

Although not an inherent risk of the study intervention or study procedures, participants for this study may have depression as determined through completion of the PHQ-9 questionnaire. As such, these participants may have suicidal ideation at screening or develop suicidal ideation during the course of the study. We have already put into place a protection protocol for just this event in our ongoing studies in HIV-infected and HIV-uninfected depressed patients (please see Appendix at end of this protocol for the full Suicide Management Plan). If a participant reports having thoughts of being better off dead or of hurting him/herself (i.e., responds with a 1, 2, or 3 to PHQ-9 Item #9 or spontaneously reports suicidal ideation), the visit will be immediately stopped, and the research assistant will interview the participant to complete the Patient Suicidality Form (see Appendix). If the participant answers “no” to all three suicide questions or if the patient answers “yes” only to Question 3 (previous attempt) and the most recent attempt was  $\geq$  10 years ago, the visit will proceed as normal, and the completed Patient Suicidality Form will be given to the principal investigator.

If the participant answers “yes” to any of the three questions (for Question #3 the previous attempt must be within the past 10 years), the research assistant will immediately contact the principal investigators. [name] (a clinical psychologist) and [name] (a physician) will review the case as soon as possible, but no later than the same day, to determine the appropriate course of action (e.g., immediately contact the patient’s primary care provider, primary HIV provider, clinical social worker, or care coordinator, consult with clinicians at Midtown Community Mental Health Center or with the psychiatrists assigned to the LifeCare clinic, and/or escort the patient to the Crisis Intervention Unit at Eskenazi Health). Additional authorities, including the police, may be contacted if immediate harm is of concern. Participants may be withdrawn from the study.

A direct correspondence by phone call and email will also be sent to the potential participant’s HIV primary provider notifying him/her of the situation (see below).

If an enrolled participant reports having thoughts of being better off dead or of hurting him/herself during any telephone calls (e.g., a scheduling call or a call to the study team initiated by the participant), the exact same procedures as outlined above will immediately be initiated. Please see the Appendix for the full Suicide Management Plan.

Because it is unknown if insomnia therapy (or lack thereof) results in somatic adverse events in antiretroviral-treated HIV-infected patients, we will also carefully document Grade 3 or 4 level toxicities defined using the Division of AIDS Table for Grading Adult Adverse Experiences. Clinical management decisions and decisions to discontinue participants from the trial will be made by the principal investigator(s) in conjunction with the participant’s primary caregiver; care plans and outcomes must be included in the source documentation.

All serious adverse events (SAEs) will be documented on CRFs with unexpected SAEs forwarded to the IU IRB within 10 working days of the event and the remainder to be documented on the annual continuing review.

## 8.0 CRITERIA FOR STUDY DISCONTINUATION

- Request by the participant to withdraw
- Request of the primary care provider if s/he believes the study is no longer in the best interest of the participant
- If the participant is found to be pregnant or begins breastfeeding during the course of this study
- If the participant develops a fever, need for systemic therapy for acute or serious illness, or hypotension after screening that precludes completion of the study visits within the allowed timeframes
- Requirement for prohibited concomitant medication(s)
- Clinical reasons believed life threatening by the physician
- Participant, as judged by the investigators, to be at risk of failing to comply with the provisions of the study protocol as to cause harm to self

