### 3.4 Week 12 Visit (70-120 days after Entry/Randomization Visit)

The SHUTi intervention and the internet sleep education/hygiene Active Control will be implemented between Entry/Randomization and Week 12. A UPT will be performed for women of reproductive potential; if positive, study participation will end and no further study procedures will be performed at this visit. Otherwise, once again, medical/psychiatric records, current medications, and current behavioral therapies will be reviewed and recorded. Weight and vital signs will be measured and recorded. All participants will complete a questionnaire battery containing the following: standard questions assessing demographics, medical/psychiatric history, sleep mediation use, insomnia treatment satisfaction, and insomnia care received outside of the trial; ISI; PSQI; DBAS-16; PHQ-9; SCL-20; GAD-7; PROMIS® Fatigue Short Form; AUDIT; PEG-3; and SF-36. The questionnaire battery will also include validated scales assessing physical activity level, tobacco use, illicit drug use, and medication adherence. The questionnaire battery will be administered on a computer in private with availability of the study team to assist only when asked by the participant. The participant may refuse to complete any of the questionnaire items.

We will then obtain again whole blood samples for laboratory testing of the inflammation biomarkers of interest and for updated HIV-1 RNA levels and CD4 cell counts. We will also archive blood and samples for future testing if consent for this is provided by the participant.

Participants who exhibit elevated depressive symptoms (PHQ-9  $\geq 10$ ) will be urged to follow-up with their primary HIV provider and/or clinical social worker regarding their depression.

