### 3.5 Week 24 Visit/Closeout (150-210 days after Entry/Randomization Visit)

At this final/closeout study visit, a UPT will be performed for women of reproductive potential; if positive, study participation will end and no further study procedures will be performed at this visit. Otherwise, once again, medical/psychiatric records, current medications, and current behavioral therapies will be reviewed and recorded. Height, weight, and vital signs will be measured and recorded. All participants will complete a questionnaire battery containing the following: standard questions assessing demographics, medical/psychiatric history, sleep mediation use, insomnia treatment satisfaction, and insomnia care received outside of the trial; ISI; PSQI; DBAS-16; PHQ-9; SCL-20; GAD-7; PROMIS® Fatigue Short Form; AUDIT; PEG-3; and SF-36. The questionnaire battery will also include validated scales assessing physical activity level, tobacco use, illicit drug use, and medication adherence. The questionnaire battery will be administered on a computer in private with availability of the study team to assist only when asked by the participant. The participant may refuse to complete any of the questionnaire items.

We will then again obtain whole blood samples for laboratory testing of the inflammation biomarkers of interest and for updated HIV-1 RNA levels and CD4 cell counts. We will also archive blood and samples for future testing if consented by the participant.

Participants who exhibit elevated depressive symptoms (PHQ-9  $\geq 10$ ) will be urged to follow-up with their primary HIV provider and/or clinical social worker regarding their depression. In addition, the study team will notify the primary HIV provider that his/her patient has completed participation in our trial and if the participant still has clinically significant insomnia (ISI  $\geq 8$ ). The study team will also provide a list of local mental health services to the patients' primary HIV providers or social workers. After the procedures for this study visit have been performed, participation in this study will end, with no further active follow-up apart from notification of final study results.

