##### 4.2 Exclusion Criteria

- 4.2.1 Inability to complete written, informed consent.
- 4.2.2 Inability to read and understand English as seen on a computer screen.
- 4.2.3 Incarceration at the time of any study visit.
- 4.2.4 Active suicidality at Entry, as determined by the patient's HIV provider or social worker following a positive response (1, 2, or 3) to PHQ-9 Item #9 and a positive response (yes) to one or more of the three questions (for Question #3, the previous attempt must be within the past 10 years) on the Patient Suicidality Form (see Appendix).
- 4.2.5 Diagnosed disease or process, besides HIV infection, associated with increased systemic inflammation (including, but not limited to, systemic lupus erythematosus, inflammatory bowel diseases, or other collagen vascular diseases).

NOTE: Hepatitis B or C co-infections are NOT exclusionary, but treatment for hepatitis C cannot be provided during study participation.

- 4.2.6 End stage renal disease requiring renal replacement therapy (dialysis, transplantation).
- 4.2.7 Known or suspected malignancy requiring systemic treatment within 180 days of the Entry Visit.

NOTE: Localized treatment for skin cancers is not exclusionary.

- 4.2.8 Therapy for serious medical illnesses within 14 days prior to the Entry Visit.

NOTE: Therapy for serious medical illnesses that overlaps with a study visit will result in postponement of that study visit until the course of therapy is completed; postponement outside of the allowed study visit timeframe will result in study discontinuation.

- 4.2.9 Pregnancy or breastfeeding during the course of the study.
- 4.2.10 Receipt of investigational agents, cytotoxic chemotherapy, systemic immunosuppressive therapies, systemic glucocorticoids (of any dose), or anabolic steroids at the Entry Visit.

NOTE: Physiologic testosterone replacement therapy or topical steroids is not exclusionary. Inhaled/nasal steroids are not exclusionary as long as the participant is not also receiving HIV protease inhibitors.

- 4.2.11 Active drug use or dependence that, in the opinion of the investigator, would interfere with adherence to study requirements.
- 4.2.12 History of bipolar disorder or a psychotic disorder, including schizophrenia.

NOTE: Depressive disorders are not exclusionary.

- 4.2.13 Current sleep disorder diagnosis other than insomnia disorder (e.g., sleep apnea).

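### Need for a prohibited drug is listed as a ground for study discontinuation with no limit on timing or duration, so a short, finished course can cost an observable Week 24 hsCRP

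*Protocol*

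**What the plan says.** Section 8.0 of the protocol gives "Requirement for prohibited concomitant medication(s" as a criterion for study discontinuation and adds no condition. The acute-illness line in the same list is conditional: it applies to illness "that precludes completion of the study visits within the allowed timeframes".

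Section 5.3 names the prohibited drugs: investigational agents, cytotoxic chemotherapy, systemic immunosuppressants, systemic glucocorticoids, anabolic steroids and hepatitis C drugs. Its exceptions concern route (topical, inhaled or nasal steroids) and physiologic testosterone replacement. None concerns duration, so a short oral steroid course counts.

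Three other rules bear on the point:
- Section 7.0 says that "decisions to discontinue participants from the trial will be made by the principal investigator(s", together with the primary caregiver.
- The NOTE to 4.2.8 postpones a visit that overlaps therapy for serious illness, and adds that "postponement outside of the allowed study visit timeframe will result in study discontinuation".
- Section 6.2.5 has prescription medications that are started or stopped "taken since the Entry Visit will be recorded on CRFs with start and stop dates".

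The primary analysis (protocol 9.1; SAP, Statistical Analyses) is an intention-to-treat ANCOVA of Week 24 hsCRP adjusted for baseline. Section 9.10 keeps everyone as randomized, whatever the completeness of their data. Section 9.2 and the SAP call for multiple imputation if more than 10% of data are missing. Neither document describes a blood draw after discontinuation.

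**The concern.** The evident purpose of the 5.3 list is to keep drug effects out of the biomarkers. That purpose is served at the time of a draw. It does not require ending follow-up for someone whose course finished months before the draw. The protocol has a proportionate tool in the 4.2.8 NOTE, postponement within the visit window, but applies it only to serious-illness therapy.

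At stake is the primary outcome for the people affected. They remain in the ITT set, but the plan gives no route to observing their Week 24 value. The need for steroids, immunosuppressants or chemotherapy may itself be related to inflammation, so these values may not be missing at random. Protocol 9.2 mentions sensitivity analyses if missingness differs but does not specify them, and the SAP's missing-data paragraph omits them. This is missing data that the plan creates itself and could avoid, in a trial whose stated goal is to estimate effect sizes.

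**Working it through.** **Timing.** Take a five-day glucocorticoid course started on day 28 and over by day 33. Section 3.5 sets the Week 24 window at days 150 to 210. The gap from end of course to draw is 150 − 33 = 117 days to 210 − 33 = 177 days. The course also ends before the Week 12 window opens on day 70, so it need not overlap any visit. If the 8.0 line were applied at once, this person's only hsCRP would be the baseline value, which is already the ANCOVA covariate.

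**Expected missingness.** Section 9.5 randomizes 50 and expects 40 to complete: (50 − 40)/50 = 20%. This exceeds the 10% trigger in 9.2, so multiple imputation is the likely branch.

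**Reproducing the plan's figure.** Inputs from 9.5: SD 4.87 mg/L, baseline to Week 24 correlation 0.64, 20 per arm, 80% power. The two-sided alpha of 0.05 is in 9.1.
- Residual SD = 4.87 × √(1 − 0.64²) = 3.742 mg/L.
- Noncentral t with df = n₁ + n₂ − 3 = 37 gives a detectable difference of 3.40 mg/L. The plan states 3.41, so the figure reproduces.

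**What retention would buy.** The documents give no rate of 5.3 drug use, so the number retained is an assumption. Suppose one or two such people per arm (4% or 8% of 25) are observed in addition to the planned 20, or one person in one arm only. The 95% CI half-width is t(0.975, df) × 3.742 × √(1/n₁ + 1/n₂).

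| Observed per arm | Detectable difference, mg/L | Power at 3.41 mg/L | 95% CI half-width, mg/L |
|---|---|---|---|
| 20 and 20 (plan) | 3.40 | 80.1% | 2.40 |
| 20 and 21 | 3.36 | 81.1% | 2.37 |
| 21 and 21 | 3.32 | 82.1% | 2.34 |
| 22 and 22 | 3.24 | 83.9% | 2.28 |

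For washed-out courses the gain is therefore modest precision. No bias figure can be derived from the documents.

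**The case against.** The strongest reply is that the 8.0 line need not be read so broadly. A requirement for a concomitant drug can mean a current or continuing need, and 7.0 leaves decisions to the investigators with the caregiver. A short course for serious illness might be handled under the 4.2.8 NOTE. This stands in part. A reader might infer that the primary outcome is automatically lost after any 5.3 drug, and the documents do not support that: discretion exists, the person stays in the ITT set, and imputation may fill the gap. But 7.0 neither limits the 8.0 line nor provides for a later draw.

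Other stronger readings also fail:
- *That sections 3.4 and 3.5 define discontinuation as no further blood draws.* The 3.4 text, "if positive, study participation will end and no further study procedures will be performed at this visit", concerns a positive pregnancy test and that visit. The 3.5 text, "participation in this study will end, with no further active follow-up apart from notification of final study results", describes normal closeout after the Week 24 procedures. The gap is that no text covers draws after early discontinuation.
- *That the entry rules are simply looser.* Section 4.2.10 does bar "systemic glucocorticoids (of any dose), or anabolic steroids at the Entry Visit", which is a point-in-time test. But 4.2.7 looks back 180 days for systemic cancer treatment and 4.2.8 looks back 14 days for serious-illness therapy.
- *That imputation would rest on baseline hsCRP alone.* No imputation model is stated, and anyone discontinued after the Week 12 visit would also have that visit's biomarkers.
- *That the arms would be affected differently.* Nothing shows this. The usual insomnia care described in 5.2 includes no 5.3 drug, and the depression follow-up prompts apply to both arms.

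It is also fair to say that on-drug hsCRP can obscure the mechanism that section 10.1 says the trial is meant to identify. Leaving such values out of an analysis is defensible. That argument does not reach a course that has washed out.

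**Conclusion.** The point holds in limited form. As written, and subject to investigator discretion, 8.0 allows a short course that ended well before Week 24 to cost an observable primary outcome and leave it to imputation. Neither document offers an alternative.

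The frequency is unknown and probably small, since 4.2.5, 4.2.7 and 4.2.10 already exclude many likely users of these drugs. No arm bias is shown. The planned 20% loss covers power, so this is not a sample-size error, and it does not contradict the ITT definition in 9.10. The precision gains above rest on an assumed one or two people retained per arm and are illustrative only. The case for change is that the loss is avoidable at little cost, while a draw not taken within its window cannot be recovered.

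**What to change.** 1. Amend 8.0 so that use of a 5.3 drug does not by itself end follow-up. Keep withdrawal of consent and the safety grounds.
2. Keep these participants in the scheduled Week 12 and Week 24 visits and draws. Postpone, within the window, a visit that overlaps a 5.3 course, as the 4.2.8 NOTE does for serious-illness therapy. If a draw is to be allowed while a course is still running at the end of the window, align the last clause of that NOTE and the illness line of 8.0.
3. Use the start and stop dates already recorded under 6.2.5 to flag hsCRP values drawn on or soon after a 5.3 drug. Set the washout by drug. A uniform 14 days borrowed from 4.2.8 would not suit all of them, given that 4.2.7 uses 180 days for systemic cancer treatment.
4. State in 9.1 and the SAP that Week 24 values after completed, washed-out courses enter the ITT ANCOVA, and that results will be reported with and without flagged values. Whether on-drug values belong in the lead analysis is a choice of estimand for the sponsor to make in advance.

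The cost is a protocol and SAP amendment, plus visits and assays for the few participants retained. No new visit type or assay is needed.
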